8.4.3 CLASSIFICATION OF AN ADVERSE EVENT

8.4.3.1 SEVERITY OF EVENT

For adverse events (AEs) not included in the protocol defined grading system, the severity of adverse events will be determined referencing the National Cancer Institute (NCI) Common Terminology Criteria for Adverse Events Version 4.0 (CTCAE). The CTCAE provides a grading (severity) scale for AEs with unique clinical descriptions of severity based on this general guidance: Grade 1: Mild AE Grade 2: Moderate AE Grade 3: Severe AE

Grade 4: Life-Threatening or Disabling AE

Grade 5: Death related to AE

8.4.3.2 RELATIONSHIP TO STUDY INTERVENTION

Adverse reaction is different than an adverse event. Suspected adverse reaction means any adverse event for which there is a reasonable possibility that the study intervention caused the adverse event. For the purposes of IND safety reporting, 'reasonable possibility' means there is evidence to suggest a causal relationship between the study intervention and the adverse event. A suspected adverse reaction implies a lesser degree of certainty about causality than adverse reaction, which means any adverse event is definitely caused by the study intervention.

Per FDA guidance a suspected adverse reaction is one that is known to be strongly associated with the study intervention, or one that is very uncommon in study population, or one shown in aggregate analysis to occur more frequently in the treatment group. Generally anticipated adverse events are not suspected adverse reactions.

Because 'reasonable possibility' can be difficult to determine, this trial uses an algorithmic approach to describing relatedness.

Algorithm to Dete	Algorithm to Determine Relatedness of Adverse Event to Study Agent			
Not Related	The temporal relationship between treatment exposure and the adverse event is unreasonable or incompatible and/or adverse event is clearly due to extraneous causes (e.g., underlying disease, environment)			
Unlikely	Must have both of the following 2 conditions, but may have reasonable or only tenuous temporal relationship to intervention.			

	 Could readily have been produced by the subject's clinical state, or environmental or other interventions. Does not follow known pattern of response to intervention.
	Must have at least 2 of the following 3 conditions
Reasonable Possibility	 Has a reasonable temporal relationship to intervention. Could not readily have been produced by the subject's clinical state or environmental or other interventions. Follows a known pattern of response to intervention.
Definitely	Must have all 3 of the following conditions
. -	 Has a reasonable temporal relationship to intervention. Could not possibly have been produced by the subject's clinical state or have been due to environmental or other interventions. Follows a known pattern of response to intervention.

8.4.4 TIME PERIOD AND FREQUENCY FOR EVENT ASSESSMENT AND FOLLOW-UP

The occurrence of an adverse event (AE) or serious adverse event (SAE) may come to the attention of study personnel during study visits and interviews of a study participant presenting for medical care, or upon review by a study monitor.

Certain adverse events will be captured and reported in WebDCU[™]. Information to be collected includes time of onset, clinician's assessment of severity, relatedness to study intervention, and time of resolution/stabilization of the event. All AEs occurring through Day 6 or Discharge, whichever comes first must be reported in WebDCU[™]. After Day 6 or Discharge, whichever comes first, only serious adverse events will be reported in WebDCUTM.All AEs will be followed to adequate resolution/stabilization or subject end of study.

8.4.5 ADVERSE EVENT REPORTING

Refer to the HOBIT safety monitoring plan for detailed information on adverse event reporting.

8.5 OPTIONAL BLOOD AND CEREBROSPINAL FLUID SAMPLE COLLECTION ANCILLARY STUDY

There are no therapeutic agents that have been shown to improve outcomes from severe traumatic brain injury (TBI). Critical barriers to progress in developing treatments for severe TBI are the lack of 1) monitoring biomarkers for assessing individual patient response to treatment and 2) predictive biomarkers for identifying patients likely to benefit from a promising intervention. Currently, clinical examination remains the fundamental tool for monitoring severe TBI and for subject selection in clinical trials. However, these patients are typically intubated and sedated, limiting the utility of clinical examination. Validated monitoring and predictive biomarkers will enable titration of the dose of promising therapeutics to individual subject response, as well as make clinical trials more efficient by enabling the enrollment of subjects likely to benefit.

The objectives of this ancillary study are:

- 1. Validate the accuracy of candidate monitoring biomarkers for predicting clinical outcome.
- 2. Determine the treatment effect of different doses of HBOT on candidate monitoring biomarkers.
- Determine whether there is a biomarker-defined subset of severe TBI that responds favorably to HBOT.

Study design: This will be a prospective observational study.

Inclusion/Exclusion Criteria: All HOBIT subjects will be eligible for enrollment in this ancillary study. Informed Consent: As with the parent HOBIT trial, participants will be enrolled in this ancillary study either with the informed consent of a legally authorized representative (LAR) or with exception from informed consent (EFIC) for emergency research under the conditions established at 21CFR50.24. Biospecimen Collection: The initial set of biospecimens (serum, plasma, CSF, DNA) will be obtained as soon as feasible after randomization to a HOBIT study arm, but no later than 24 hours from injury. Subsequent biospecimens will be obtained every 8 hours (+/- 1 hour) for the first 24 hours postenrollment. This will allow the characterization of acute changes in biomarker levels. On study days 2, 3, 5, 7 and 14 biospecimens will be obtained once a day to allow characterization of sub-acute changes in biomarker levels. If feasible, samples should be collected at 8am (+/- 2 hours) to minimize the effects of circadian rhythm on biomarker levels. In addition, during the first 5 days of the study, one set of biospecimen will be collected 4 hours after HBO treatment to examine the acute effects of HBO treatment on biomarkers. This will not apply to those randomized to non-HBOT groups. During the 6month visit, 1 tablespoon (15 ml) of blood will be collected. At each of the timepoints mentioned above, we will collect 15 cc of blood which will be processed into serum, plasma and DNA and stored in a -70 or -80 degree Celsius freezer. In addition, for subjects who have an external ventricular drain in place, we will collect, process and store 5 cc of CSF at each of these timepoints if feasible. Since subjects are unlikely to have an EVD after the first week post-injury, CSF samples will be collected only for as long as the EVD is in place.

Biospecimen Processing and Storage: Whole blood and CSF samples will be centrifuged, separated into serum, plasma, and CSF, and aliquoted and stored in a -70 or -80 degree Celsius freezer within 2 hours of phlebotomy. During the separation of plasma samples from whole blood, the buffy coat suspension (a concentrated leukocyte suspension) will be extracted and stored for DNA analysis. This will be done each time plasma is extracted from whole blood, in order to increase the DNA yield. Samples will be shipped in periodically to the NINDS Biorepository at Indiana University (BioSEND). Additional details regarding sample collection, processing and storage are in the Manual of Procedures.

Biospecimen analysis: We will measure levels blood and CSF of biomarker that are associated with TBI and TBI prognosis. These will include: Glial fibrillary acidic protein (GFAP), neurofilament light chain (NfL) and high sensitivity C-reactive protein (hsCRP).

9 STATISTICAL CONSIDERATIONS

9.1 STATISTICAL HYPOTHESES

In this phase II clinical trial we hypothesize that there is at least one treatment arm that will demonstrate neurological improvement that warrants further exploration in a confirmatory Phase III trial. The HOBIT trial uses an adaptive design for selecting the combination of hyperbaric oxygen (hyperoxia) treatment dose parameters - pressure and intervening normobaric hyperoxia [NBH]) that provides the greatest improvement in the rate of good neurological outcome versus standard care for subjects with severe traumatic brain injury (TBI). A second goal of this phase II trial is to determine if there is any factor combination of hyperoxia treatment that has at least a 50% probability of demonstrating improvement in the rate of good neurological outcome versus a control (i.e. standard care) in a subsequent phase III confirmatory trial, assuming to be 500 in the control and 500 in the novel arms (Gajewski 2016).

Treatment arms.

There are eight treatment arms defined in the trial:

	Arm	Dose (OTU)
1	Control (1.0 ATA)	N/A*
2	1.5 ATA	260
3	2 ATA	417
4	NBH (100% FiO2 at 1.0 ATA)	540
5	2.5 ATA	592
6	1.5 ATA+NBH	620
7	2 ATA+NBH	776
8	2.5 ATA+NBH	952

*NOTE : In the control arm, subjects will be at 1.0 ATA, however the percent of FiO2 will not be

regulated. Thus, it is theoretically possible that these subjects are accumulating OTUs. For the purposes of this study they will consider the "dose" to be zero and this arm will be modeled separately. The FiO2 will be recorded throughout the study. Subjects will receive at least 21% O2 outside of the chamber, but the level of oxygen supplementation may be higher though not typically exceeding 50%.

Primary Endpoint. The primary analysis will use the intention to treat (ITT) sample to compare the proportion of favorable outcomes in the 6-month dichotomized, severity adjusted, GOS-E (section 11.1 of the SAP) in each treatment arm to control dose regimen (1.0 ATA). Favorable outcome for an individual subject is defined according to a sliding dichotomy (Murray, 2005), where the definition of favorable outcome varies according to baseline prognosis. Prognosis will be defined according to the probability of poor outcome predicted by the IMPACT Core Model (Steyerberg EW, 2008); see section 11.1.2.1 of the SAP). The favorable outcome definition is more stringent for subjects predicted to do well (i.e. a low probability of poor outcome), as outlined in the Table below. The IMPACT core score will be based on the covariate as known at randomization. The primary endpoint will analyze the GOS-E at 26 weeks; intermediate measurements will be taken at 4, 13 weeks.

Seventy Aujusted GOS-E							
Probability of poor	Glasgow Outcome Scale-Extended						
Outcome on IMPACT	Upper Good Recovery	Lower Good Recovery	Upper Moderate Disability	Lower Moderate Disability	Upper Severe Disability	Lower Severe Disability	Vegetative or Death
GOS -E	8	7	6	5	4	3	2/1
0 to <0.21							
0.21 to <0.41					Poor O	utcome	
0.41 to <0.56		Favorable	e Outcome				
0.56 to ≤1.0							

Severity Adjusted GOS-E

That is, the primary outcome of favorable GOS-E outcome is derived as follows:

 $Y = \begin{cases} 1 & if \quad 0 \le Impact < 0.21 \text{ and } GOS - E \text{ is } \ge 7\\ 1 & if \quad 0.21 \le Impact < 0.41 \text{ and } GOS - E \text{ is } \ge 6\\ 1 & if \quad 0.41 \le Impact < 0.56 \text{ and } GOS - E \text{ is } \ge 5\\ 1 & if \quad 0.56 \le Impact \le 1 \text{ and } GOS - E \text{ is } \ge 4\\ 0 & otherwise \end{cases}$

Primary Analysis. The primary analysis is of the GOS-E response at 6 months will use the sliding dichotomy methodology. To assess efficacy, the treatment groups will be compared with respect to the proportion with favorable outcome. The primary analysis will be that a treatment arm is superior to the control arm, meaning that the posterior probability that the rate of response with GOS-E is greater for one experimental arm compared to the control arm. The final analysis will also identify the best treatment arm to advance to a future Phase III trial for confirmation of superiority to the control arm. Specifically, the currently proposed Phase II trial will be considered conclusive if one of the three following cases occur:

1. Early Success: If at any interim analysis the most likely arm has at least a 0.975 posterior probability of being better than control. Minimum subjects enrolled before the study can stop for early success is 116.

2. End of Enrollment Success: If at the conclusion of accrual, the most likely arm has at least a 0.85 posterior probability of being better than control and this same best arm has at least a 0.5 posterior probability of leading to a successful Phase III trial.

3. Early Futility: If at any interim analysis the maximum probability of active dose being better than control by more than 0.10 across all doses is less than 0.10. Minimum subjects enrolled before the study can stop for early futility is 116.

Specific details of the models and assumptions are found in the HOBIT Statistical Analysis Plan.

9.2 SAMPLE SIZE DETERMINATION

With a maximum sample size of N=200, this design provides at least 77% power when there is improvement (effect) in favorable GOS-E outcomes for active arms over control (Table X). If the treatment arms have a medium or large effect over control, the power is respectively 92% and 98%. If the active arms have no improvement (e.g. 'none') or are worse than control (e.g. harmful) then the early futility rates are respectively 29% and 53% (Table X). Results for other assumptions including other scenarios, longitudinal assumptions, and accrual rates are presented in the HOBIT Statistical Analysis Plan.

Although the maximum sample size is N=200, the simulations conducted indicate the average sample size under the complete null scenario (effect is 'none') is 183 and under the scenarios with small, medium, and large effect of active arms relative to control is respectively 184, 172, and 155. For the harmful scenario the sample size is 169. The type I error probability (incorrectly identifying treatment(s) to success that are truly no better than control) for the complete null scenario ('none') is 0.21.

Scenarios (Accrual is 1.6 subjects/week)					
	Proportion of TBI Subjects with Favorable GOS-E Outcomes (6 months)				
Arm	Scenario 1 None	Scenario 2 Small	Scenario 3 Medium	Scenario 4 Large	Scenario 5 Harmful
Control	0.40	0.40	0.40	0.40	0.40
1.5 ATA	0.40	0.49	0.54	0.59	0.35
2.0 ATA	0.40	0.50	0.55	0.60	0.35
1.0 ATA+NBH	0.40	0.51	0.56	0.61	0.35
2.5 ATA	0.40	0.52	0.57	0.62	0.35
1.5 ATA+NBH	0.40	0.53	0.58	0.63	0.35
2.0 ATA+NBH	0.40	0.54	0.59	0.64	0.35
2.5 ATA+NBH	0.40	0.55	0.60	0.65	0.35
Pr{Success}	0.21	0.77	0.92	0.98	0.08
Pr{Futility}	0.29	0.03	0.01	0.00	0.53
Sample Size	183	184	172	155	169
Trial Duration (wks)	133	140	133	123	118

Table X- Power, Futility, Sample Size, and Trial Duration for Varying Effects for Various Scenarios (Accrual is 1.6 subjects/week)

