OB.	JECTIVES	ENDPOINTS	JUSTIFICATION FOR ENDPOINTS					
Prir	mary							
effe par pro	definitively determine the most ective hyperbaric oxygen therapy radigm and to predict the obability that this treatment will ult in a successful Phase III trial.	Proportion of subjects with favorable outcome at 6-months (Severity adjusted GOS-E)	GOS-E is the most frequently used functional outcome measure for TBI studies.					
Sec	condary							
1.	Determine the effect of HBO treatment on the duration of ICP elevation.	The level and duration of intracranial hypertension (ICP>22 mmHg) will be measured.	Intracranial hypertension is the leading cause of death and deterioration in the first week following TBI (Jull, 2000).					
2.	Determine the effect of HBO treatment on therapeutic intensity level (TIL) scores for controlling intracranial pressure (ICP).	Therapeutic intensity level (TIL) scores. This documents the level of therapies used to control ICP and will be tracked daily during the treatment period.	TIL scores will quantify the intensity of treatment required to control ICP between treatment groups.					
3.	Determine the effect of HBO treatment on brain tissue partial pressure of oxygen (PO2)monitoring.	The level and duration of brain tissue hypoxia (brain tissue PO2 <20 mmHg).	Brain tissue PO2 levels <20mmHg correlate with poor outcome in severe TBI (VanDen Brink, 2000).					
4.	Compare the type and incidence of SAEs between hyperoxia treatment arms and control.	SAEs include: Pneumothorax secondary to HBO, pulmonary dysfunction defined as PaO2/FiO2 (PF) ratio<200, pneumonia, and seizures during HBO.	Special scrutiny is required for complications related to hyperoxia treatment.					

5.	Estimate the effect of peak brain tissue PO2 during hyperbaric oxygen treatment on GOS-E at 6-months.	Dichotomized GOS-E.	Level of O2 achieved in the brain during HBO treatment may correlate with outcome.

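### Section 9.2 presents 77% as a lower bound on power for any improvement, but it is the success probability of one scenario in which all seven active arms gain 9 to 15 points

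*Protocol*

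**What the plan says.** The power claim in protocol section 9.2 opens with "With a maximum sample size of N=200" and continues that "this design provides at least 77% power when there is improvement (effect) in favorable GOS-E outcomes for active arms over control". It then points to Table X, and the next sentence gives 92% and 98% for medium and large effects.

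These rows of Table X matter here (columns: none, small, medium, large, harmful):

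- "Control 0.40 0.40 0.40 0.40 0.40"
- lowest active dose: "1.5 ATA 0.40 0.49 0.54 0.59 0.35"
- highest active dose: "2.5 ATA+NBH 0.40 0.55 0.60 0.65 0.35"
- "Pr{Success} 0.21 0.77 0.92 0.98 0.08"

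The five arms between these two rise by one point per step in each beneficial scenario. Section 9.2 adds that results for other scenarios are in the SAP.

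Section 9.1 states the hypothesis: "we hypothesize that there is at least one treatment arm that will demonstrate neurological improvement". The primary objective in the section 3 table is to "definitively determine the most" effective regimen. Objective 2 in the synopsis (section 1.1) speaks only of selecting the combination most likely to succeed later, and section 9.1 sends the chosen arm to Phase III for confirmation.

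**The concern.** The sentence in 9.2 ties its minimum to improvement as such, with no size of effect and no number of effective arms. Every beneficial column of Table X improves all seven arms, and none by less than 9 points. No column has a smaller common gain, and none sets an effective arm beside ineffective ones. The hypothesis in 9.1 requires only one effective arm, so it covers configurations less favourable than any in the table.

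A reader of the power paragraph could take a negative trial as having had at least a 77% chance of detecting any real benefit. For modest common gains, or for one effective regimen among seven, the chance would be much lower.

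**Working it through.** **Step 1. Which scenario gives 77%.** In the Pr{Success} row, 0.77 stands under Scenario 2. The active-arm rates there are 0.49, 0.50, 0.51, 0.52, 0.53, 0.54 and 0.55 against 0.40. The gains are 9, 10, 11, 12, 13, 14 and 15 points, with mean 84/7 = 12.

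**Step 2. Whether it can be a floor.** Scale the Scenario 2 gains by a factor t from 0 to 1. At t = 0 the scenario is the complete null, with Pr{Success} 0.21; at t = 1 it is Scenario 2, with 0.77. The success probability is a continuous function of the true rates, so it takes every value between 0.21 and 0.77 along this path. Every point with t > 0 is an improvement in all seven arms. A minimum of 0.77 is therefore false on Table X's own figures. A crude linear interpolation on the mean gain, for scale only, puts a 5-point gain at 0.21 + (5/12) × (0.77 − 0.21) = 0.44.

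**Step 3. Size of the shortfall, by approximate simulation.**

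Taken from the protocol:
- burn-in of 56 (11 control, 6 in each of six active arms, 9 in the top dose)
- adaptive allocation proportional to the probability of being best
- updates every 20 subjects, stopping possible from 116, last interim at 176, final at 200
- early success at 0.975; final success at 0.85 together with a 0.5 probability of Phase III success with 500 per arm
- the futility rule of section 9.1

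Assumed, because not shown:
- the arm model (hierarchical shrinkage, or smoothing over dose order) and its shrinkage SD
- the control share after burn-in
- the outcome lag (0, or 26 weeks × 1.6 per week ≈ 42 subjects)
- two-sided 0.05 for Phase III

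The three settings closest to the stated success row, all with SD 0.3 and 2,500 trials per scenario (Monte Carlo SE at most √(0.25/2500) = 0.01), gave:

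| Scenario | Table X | Smoothed, no lag, control matched to top arm | Hierarchical, lag 42, control 33% | Hierarchical, no lag, control 33% |
|---|---|---|---|---|
| None | 0.21 | 0.23 | 0.25 | 0.22 |
| Small | 0.77 | 0.77 | 0.79 | 0.78 |
| Medium | 0.92 | 0.89 | 0.92 | 0.93 |
| Large | 0.98 | 0.97 | 0.98 | 0.98 |
| Harmful | 0.08 | 0.08 | 0.08 | 0.06 |
| All seven +9 | – | 0.64 | 0.65 | 0.64 |
| All seven +5 | – | 0.45 | 0.43 | 0.47 |
| Only top dose +15 | – | 0.53 | 0.44 | 0.45 |
| Only a middle dose +15 | – | 0.34 | 0.39 | 0.42 |
| Only top dose +20 | – | 0.69 | 0.53 | 0.59 |
| Only a middle dose +20 | – | 0.42 | 0.50 | 0.54 |
| Only top dose +25 | – | 0.83 | 0.65 | 0.73 |
| Only a middle dose +25 | – | 0.55 | 0.62 | 0.70 |

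Over all settings with SD 0.3 to 0.4, one arm at +15 gave 0.30 to 0.57. A separate set of runs (control share 20%, 3,200 trials per scenario) gave 0.36 to 0.43 for all arms at +5 and 0.41 to 0.43 for one arm at +15. It returned only 0.68 to 0.73 in Scenario 2, so it probably runs somewhat low.

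The match to Table X is no independent confirmation, because the shrinkage SD and control share were chosen for closeness to the stated success row. Mean sample size in Scenario 2 was 169 to 177 against the stated 184.

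**Step 4. Two cross-checks for one arm at +15.**
- Fully independent arms gave 0.65 to 0.67. Their null success rate was 0.37 to 0.44, which is incompatible with the stated 0.21.
- A fixed comparison with assumed sizes of 40 in the active arm and 60 in control, 0.55 v 0.40, one-sided 0.15: SE = √(0.55 × 0.45/40 + 0.40 × 0.60/60) = 0.101; 0.15/0.101 − 1.036 ≈ 0.45; power ≈ 0.67, before any penalty for choosing among arms.

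No setting tried reached 0.77 for one arm at +15.

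**The case against.** The strongest reply is that the sentence refers to Table X, speaks of active arms in the plural, and is followed by 92% and 98%. On that reading 77% is the minimum of the three beneficial columns, and the table beside it prints every arm's rate. This stands in part: nothing is miscalculated, and a careful reader can recover the condition. It does not make the sentence true, because the stated condition is improvement and Table X shows that this is not enough.

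The second reply is that other scenarios are assigned to the SAP. That stands. A one-arm or 5-point scenario may be reported there, and its absence from the protocol is no fault. But if the SAP holds scenarios with lower power, the sentence in 9.2 contradicts them.

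Three stronger readings are tempting, and the documents do not support them:

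- **That power is 40 to 55% under the trial's own hypothesis.** The hypothesis is at least one effective arm. Exactly one is its least favourable case, and all seven improving satisfies it equally. No such figure can be derived from the protocol, and it means nothing without an effect size: the best-matching models give 0.42 to 0.69 at +20 and 0.55 to 0.83 at +25, so a single large effect can exceed 77%.
- **That the best arm will usually be missed.** Simulated rates of choosing the true best arm depend heavily on the assumed model and on final arm sizes that the protocol does not give. Neighbouring arms in Table X differ by one point, so choosing a neighbour costs little.
- **That the go/no-go decision is affected.** That decision rests on the posterior thresholds in section 9.1, not on the 77% sentence.

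**Conclusion.** The power property is misstated. 77% belongs to Scenario 2, with all seven active arms 9 to 15 points above control, and is not a lower bound for improvement in general. This follows from Table X alone and needs no simulation.

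The size of the shortfall rests on assumed models, because the SAP's model and the control share after burn-in are not shown. Under those assumptions, success is roughly 0.36 to 0.47 when all arms gain 5 points and roughly 0.30 to 0.57 when a single arm gains 15. The direction held in every model tried for these two cases; the exact values should not be quoted as properties of the design.

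The section 3 wording is a minor inconsistency with Objective 2 and with the planned Phase III confirmation.

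**What to change.** In section 9.2, replace the claim with: *77% power if all seven active arms improve by 9 to 15 points over control (Scenario 2, Table X); power is lower for smaller effects or when fewer arms reach gains of this size; see the SAP for other scenarios.* No extra columns are needed in Table X.

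In the section 3 objectives table, replace the claim of definitive determination with Objective 2's aim of selecting the combination most likely to show improvement in a later confirmatory trial.

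Both are wording changes that leave the design, the decision rules and the tabulated figures untouched. The only cost is a slightly less favourable statement of power.
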